H2: Care partners who receive STELLA-FTD with ABC training (test group) will have significantly higher self-efficacy scores ⁽³⁾ than the control group.

H3: Care partners with higher self-efficacy will have lower burden scores.

H4: Self-efficacy will partially mediate the relationship between ABC training and burden.

Aim 3: Prepare STELLA-FTD for NIH Stage 2 testing: standardize materials and fidelity assessment processes.

3) Background

Importance of FTD and care partner burden. Dementia due to frontotemporal neurodegeneration (FTD) affects adults at the apex of their work and family life, with the peak incidence between the ages of 45 and 65 ⁽⁴⁾. FTD disorders are a heterogeneous group of dementias characterized by progressive impairments in behavior, language and motor function due to degeneration in brain regions responsible for executive function, social comportment and language ⁽⁵⁻⁸⁾. FTD includes several subtypes, the most common are behavioral variant frontotemporal dementia (bv-FTD) and primary progressive aphasia (PPA) ^(4-6, 8) (in this proposal, **we group all FTD dementias together and use the term, "FTD"**). The combination of behavior and language deficits causes substantial burden for the persons caring for those with FTD, *the family care partners* ^(8, 9).

Care partners report burden in all types and phases of FTD. In the early stages, memory is often preserved, contributing to diagnostic confusion and delay with accompanying family stress and frustration (8, 10-13). With disease progression, behavioral symptoms such as irritability, anxiety, agitation, apathy and disinhibition become more prominent, predicting higher levels of care partner burden (8, 13). Behavioral symptoms occur in all FTD types, but tend to happen at different phases in the disease trajectory. For example, in bv-FTD, behavioral symptoms are prominent early on, but in PPA, the symptoms are more pronounced in the later stages. Along with the behavioral changes, language, motor and global cognitive deficits further contribute to care partner burden (6, 8, 11). Of note, the FTD-related symptoms and their impact on daily and social function lead to care partner burden that is considered greater than that experienced by those who care for family members with Alzheimer's disease (10).

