Care Partners may fill out weekly "Orbit" surveys that were developed by the Oregon Roybal Center for CAre Support Translational Research Advantaged by Integrating Technology (ORCASTRAIT), housed at the Oregon Alzheimer's Disease Research Center. The survey includes the "ORCASTRAIT Care Partner Weekly Survey," which measures Care Partner emotional and physical strain, The 4-item ZBI, a brief measure of burden ($\alpha=.78$),³¹ medication use, likelihood of placing their care recipient into long term care (e.g., assisted living, memory care), and frequency of contact with both their and their family member with dementia's clinical providers. Also included in the Orbit survey is the "ORCASTRAIT Caregiver Cost Survey," which measures out-of-pocket costs. The two surveys will take approximately 1-15 minutes (total) to fill out and will be emailed to the Care Partners weekly using REDCap or Qualtrics servers.

If the Care Partners drop out of the study, we will ask them to complete the Exit Survey so we can get their feedback.

Table 3. STELLA-FTD Measures

Enrollment	
Demographics	Age, sex, gender identity, marital status, race, ethnicity, rurality, etc.
FTD characteristics	Diagnosis, year of diagnosis, daily hours of caregiving
CDR Plus NACC FTLD ⁽⁶⁾	Person with FTD disease severity, behavioral & language symptoms (data provided by Care Partner)
Baseline Assessment (Week 1)	
Revised Memory & Behavioral Problems Checklist (RMBPC) ⁽²⁾	Measure of frequency and reactivity to behavioral and psychological symptoms of dementia, α 0.86
Self-efficacy for symptom management and support service use ⁽³⁾	10-item scale, α 0.77
Preparedness for Caregiving Scale ⁽⁶³⁾	8-item measure, α 0.91
Ten Item Personality Inventory ⁽⁶⁴⁾	Measures intro- and extraversion (α .45-.68)
Pre-intervention Assessment (Week 4)	
RMBPC ⁽²⁾	(as above)
Self-efficacy for symptom management and support service use ⁽³⁾	
Preparedness for Caregiving Scale ⁽⁶³⁾	
Service and support use survey	
Personalized Target Behavior Survey ^(29, 30)	Measures frequency and reactivity of up to 3 personalized behaviors identified by care partners
Mid-Intervention Assessment (Week 8)	
RMBPC ⁽²⁾	(as above)
Post Assessment 1: Same as Pre-Intervention Assessment Plus:	
STELLA-FTD contact ⁽²⁹⁾	STELLA-FTD care partner contact with peers
STELLA-FTD Experience Survey ⁽²⁹⁾	16-item- survey on satisfaction, privacy, ease of use
Post Assessments 2 & 3: Same as Pre-Intervention Assessment Plus:	

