Data from this study may be shared with other investigators for future research studies through the data repository (OHSU IRB # 6845). Data from the repository will be shared with other investigators according to the IRB approved repository policy.

8) Data Analysis

Data Analysis. This study will generate a comprehensive set of data that tests STELLA-FTD's preliminary efficacy and its mechanism of action. In all final models, we will examine the relationships between diagnosis type, demographic and biological characteristics (e.g., sex, race, education) and the outcome and process variables.

Aim 1. Test the preliminary efficacy of STELLA-FTD in this NIH Stage 1B clinical trial by comparing burden (reactivity on the RMBPC (2)), between two care partner groups: the test group, who receives training in the ABC analytic approach and the control group that does not.

H0: There will be no change on the RMPBC reactivity score in the two pre-intervention assessments (completed at weeks 1 and 4) in both test and control groups. The primary outcome for H0 is the RMBPC (2) reactivity score. First, we will provide both statistical and graphical evaluation for the distributions of the primary outcome and transform the data to normalized values if needed (e.g., log transformation). We will descriptively explore the RMBPC (2) reactivity score at weeks 1 and 4 for each group and the primary outcome will be reported as mean (SD). To test whether reactivity scores change from week 1 to week 4, paired t-tests will be used to compare scores within each group. Then, we will compute the change scores between week 1 and week 4 for each participant and the normality of change score will be assessed. If normality assumption is violated, we will perform a data transformation. To test the difference in change scores between weeks 1 and 4, we will conduct a two-sample t-test of the change score between the test and control groups. All of the results will be considered significant at $\alpha = 0.05$. We expect no significant change between weeks 1 and 4 within each group and the change scores will not be significantly different between the test group and control group.

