H1: Upon completion of the STELLA-FTD 8-week intervention, care partners in the test group will have significantly lower (better) burden scores than those in the control group. For H1, we will employ a mixed effects model to analyze whether the change in reactivity on the RMBPC (2) differs across groups (test vs. control) over the intervention period. Two fixed effects will be included in the model: 1) Group effect will be included as a dichotomous categorical variable (test vs. control); 2) Time effect will be included as a continuous variable. The interaction between group and time (group x time) will also be included. Random intercepts will be incorporated for subject specificity in the model to account for clustering effect within subject over time. We will perform a hypothesis test for the coefficient of the interaction term (group x time) to assess the difference in change on primary outcome in the intervention group as compared to control group, over time. We will extend the model to include diagnosis type (e.g., PPA, bv-FTD), frequency of behavioral symptoms as measured on the RMBPC (2), socio-demographic covariates (e.g. sex, age, sex, education) and external support group use. Results will be considered significant at $\alpha = 0.05$, with two-sided test. Similar analyses will occur at Week 20 and 36.

Aim 2. Test the mechanism of action of STELLA-FTD by isolating the ABC training component (the behavior change technique) and determining its relationship to self-efficacy (the intervention target) and burden (the primary outcome) (Figure A).

The statistical analyses for Aim 2 will be carried out in three steps to investigate the mediated effect of self-efficacy ⁽³⁾ on the association between intervention and primary outcome, the RMBPC ⁽²⁾ reactivity score.

H2: Care partners who receive STELLA-FTD with ABC training (the test group) will have significantly higher self-efficacy scores ⁽³⁾ than the control group. To test H2 in the first step, we will employ a similar mixed effect model as H1. The mixed effect model analyses will be performed on total self-efficacy score as the outcome. A hypothesis test for the coefficient of the interaction term (group x time) will be performed to assess the difference in change on self-efficacy score in the test group as compared to control group, over time.

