H3: Care partners with higher self-efficacy will have lower burden scores. In the second step to test for H3, we will construct a mixed effect model on the RMBPC ⁽²⁾ reactivity score as the outcome. Total self-efficacy score ⁽³⁾ will be included as a continuous independent variable; time will be included as a continuous variable. The interaction between total self-efficacy score and time (self-efficacy score x time) will also be included. Random intercepts will be incorporated for subject specificity in the model to account for clustering effect within subject over time. A hypothesis test for the coefficient of the interaction term (self-efficacy score x time) will be performed to assess the relationship between change on primary outcome (RMBPC reactivity score ⁽²⁾) and total self-efficacy score ⁽³⁾, over time.

H4: Self-efficacy will partially mediate the relationship between ABC training and burden. In the third step, a mixed effect model on RMBPC reactivity score ⁽²⁾ will be constructed based on the model in H1. We will extend the established model in H1 to include total self-efficacy score as a continuous covariate and the interaction term between total self-efficacy score and time (self-efficacy score x time) will also be included. We expect the interaction term coefficient (group x time) in model for H1 will be significant, and the coefficient of the interaction term between group and time (group x time) will be attenuated and may become non-significant after extending the model to add total self-efficacy score as a covariate and the interaction between total self-efficacy score and time (total self-efficacy score x time). This will indicate that the self-efficacy has a mediated effect on the association between the intervention and change in the primary outcome (RMBPC reactivity score ⁽²⁾) as compared to the control group. We will also extend these models to include diagnosis, frequency of behavioral symptoms as measured on the RMBPC ⁽²⁾, socio-demographic covariates and preparedness (78). All of results above will be considered significant at $\alpha = 0.05$, with two-sided tests.

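### Enrolment disease severity is collected but enters no planned model, so the non-randomised H3 and H4 analyses leave residual confounding by severity unaddressed

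*Combined protocol and SAP*

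**What the plan says.** Table 3 (section 6, Procedures) lists two relevant items at enrolment. One is the CDR plus NACC FTLD, described as "Person with FTD disease severity, behavioral & language symptoms (data provided by Care Partner". The other, under FTD characteristics, is "Diagnosis, year of diagnosis, daily hours of caregiving".

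Section 8 (Data Analysis) describes covariates in three places:

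- **General statement:** "In all final models, we will examine the relationships between diagnosis type, demographic and biological characteristics (e.g., sex, race, education", in relation to the outcome and process variables.
- **Aim 1, H1:** "We will extend the model to include diagnosis type (e.g., PPA, bv-FTD), frequency of behavioral symptoms as measured on the RMBPC (2), socio-demographic covariates", followed by use of outside support groups.
- **Aim 2, end of H4:** "We will also extend these models to include diagnosis, frequency of behavioral symptoms as measured on the RMBPC", followed by "socio-demographic covariates and preparedness (78".

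Neither the severity rating nor caregiving hours is named in any of them.

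H3 regresses RMBPC reactivity on self-efficacy, time and their product, with a random intercept, and tests the product term. H4 adds self-efficacy and self-efficacy by time to the H1 model and reads a shrinking group-by-time coefficient as evidence of mediation. It sets no minimum shrinkage.

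**The concern.** H3 and H4 carry the mechanism claim of Aim 2. Care partners are randomised to ABC training, not to a level of self-efficacy, so anything that drives both self-efficacy and burden can produce an association between them.

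Disease severity is a plausible common cause, and section 3 (Background) supports half of that path. It says that behavioural symptoms grow with progression, "become more prominent, predicting higher levels of care partner burden". The next sentence adds that problems with language, movement and general cognition also contribute to burden. The link from severity to self-efficacy is plausible, but the documents do not state it.

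The planned covariates cover this only in part. RMBPC frequency counts behaviours and does not measure the other deficits. Diagnosis type is not a stage, and section 3 says that behavioural symptoms come early in bv-FTD and later in PPA, so the same frequency can mean different stages in different diagnoses. The sample spans all the listed FTD diagnoses and includes advanced disease, so severity may vary widely.

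At stake is whether a significant H3 coefficient, or a shrinking group effect in H4, can be credited to self-efficacy rather than to how ill the care recipient is.

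**Working it through.** **1. The plan's own figure.** The sample size does not depend on this covariate, but it reproduces. For three measurements under compound symmetry, n per group = 2(1.960 + 0.842)² × [1 + 2 × ICC] / (3 × 0.3²).

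- ICC 0.5: 116.3, so 117.
- ICC 0.6: 127.9, so 128.

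Both match section 4. The fix leaves them unchanged.

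**2. Inputs for the illustration.**

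- From the documents: 300 × 0.85 = 255 care partners; visits at weeks 4, 12, 20 and 36; ICC 0.55 (middle of 0.5 to 0.6); two-sided alpha 0.05.
- Assumed, because the documents give no values: severity S correlates −r with self-efficacy and +r with reactivity, and adds c SD of reactivity per SD of severity over the 32 weeks from week 4 to week 36. These are relations left after the listed covariates.
- Self-efficacy has no effect on reactivity.

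**3. Model,** with t = (week − 4)/32:

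- Reactivity = r·S + c·S·t + random intercept + error
- Self-efficacy = −r·S + random intercept + error

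The analysis is H3's: a random-intercept regression on self-efficacy, time and self-efficacy by time, testing the last term.

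**4. Why the slope matters.** The part of S that self-efficacy predicts is about −r × self-efficacy, so the term c·S·t appears as roughly −r·c on self-efficacy by time. If c = 0, that bias is zero.

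**5. Rejection of the true null (1,500 trials per setting).**

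| Visits | c | r | H3 test rejects |
|---|---|---|---|
| Weeks 4–36 | 0 | 0.2–0.4 | about 4–6% |
| Weeks 4–36 | 0.1 | 0.3–0.4 | about 7–10% (highest in any run 13%) |
| Weeks 4–36 | 0.2 | 0.3 | about 20–22% |
| Weeks 4–36 | 0.3 | 0.3 | about 40% |
| Weeks 4–36 | 0.3 | 0.4 | about 57–58% |
| Up to week 12 | same rate as 0.2–0.3 | 0.3–0.4 | about 4–11% |
| Any, with S and S by time added | any | any | about 5% (4–7%) |

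The short window is milder because only 8/32 of the slope effect has accrued between weeks 4 and 12: 0.2 × 8/32 = 0.05 SD and 0.3 × 8/32 = 0.075 SD.

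**6. Does RMBPC frequency already deal with it?** A second simulation used 256 care partners, weeks 1, 4 and 12, loadings of severity on self-efficacy of 0.2 to 0.4 and on frequency of 0.3 to 0.6, a level effect of 0.3 SD and a slope effect of 0.2 SD across weeks 1 to 12. H3's test rejected in:

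- 19–40% unadjusted;
- 20–41% with frequency;
- 21–44% with frequency and a severity main effect;
- 6–9% with severity and severity by time.

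So frequency helps little here, and a severity main effect alone does not repair the interaction test. With a level effect only, rejection was 5–8%. This scenario is steep: 0.2 SD in 11 weeks is 0.2 × 32/11 = 0.58 SD over 32 weeks, about 2.9 times the 0.2 rate in step 5.

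**7. H4 in that second simulation,** with no mediation present:

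- With the slope effect, group by time shrank from −0.304 to −0.282 (0.022/0.304 = 7%) at loading 0.2, and from −0.297 to −0.254 (0.043/0.297 = 14%) at loading 0.4.
- With a level effect only, it shrank from −0.303 to −0.294 (3%) and from −0.301 to −0.281 (7%).
- With severity and severity by time added, it returned to about −0.30.

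**The case against.** The strongest reply is that the effect on the coefficient H3 actually tests depends on assumptions. Severity acting on burden level alone leaves self-efficacy by time at its nominal rate. Marked inflation needs a residual slope of 0.2 to 0.3 SD per SD, after diagnosis, frequency, socio-demographics and preparedness are adjusted for, when the whole planned treatment effect is 0.3. It also needs follow-up to week 36. H1 is framed over the intervention period with similar analyses at weeks 20 and 36, and H3's window is not stated. All of this stands, and the size of the problem must be given conditionally.

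It is also fair that the CDR item overlaps with RMBPC frequency, since Table 3 says it covers behaviour and language and is reported by the care partner. Section 3's first link from progression to burden runs through behavioural symptoms, which the plan adjusts for. This makes the existing covariates partial proxies. It does not make them sufficient, because the same section names non-behavioural deficits as a further source of burden.

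The general statement in section 8 is loosely worded, so severity is unspecified rather than excluded. But its examples illustrate demographic and biological characteristics, and the Aim 2 list is specific, so this wording does not commit the analysts to using severity.

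A reader might infer three stronger things that the documents do not support:

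- **That H1 and H2 are biased.** They compare randomised groups, so omitting severity does not confound them. Adjustment there is an optional choice for precision.
- **That caregiving hours must also be added.** No section links hours to burden or self-efficacy, and the simulations do not include them.
- **That H3 fails even without a slope effect.** With a level effect only, the self-efficacy main coefficient is significant in about 18% of trials at r = 0.3 and 52% at r = 0.4. That is not the coefficient H3 tests.

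**Conclusion.** The point holds in a limited form. A measure of severity taken before the intervention starts is available and unused. Self-efficacy is an observational exposure in H3 and H4, and the planned covariates stand in for severity only partly.

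Whether H3 is materially affected cannot be read from the documents. It ranges from no effect (level effect only, about 5%) to serious (roughly 20 to 58% false rejection with r of 0.3 to 0.4 and a 0.2 to 0.3 SD slope over weeks 4 to 36). It is mild at 0.1 SD or with visits only to week 12. For H4, the illustrated shrinkage without mediation is 3 to 7% with a level effect and 7 to 14% with a steep slope. Because H4 sets no threshold, either would count in the expected direction. To say flatly that H3 and H4 are confounded would go beyond the evidence. The supportable statement is that residual confounding by severity is left unaddressed when the data to address it are in hand.

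**What to change.** In section 8, Aim 2, add the enrolment CDR plus NACC FTLD score and its interaction with time to the extended H3 and H4 models. The interaction is needed because a main effect alone does not protect the self-efficacy-by-time test. Report the self-efficacy coefficients, and the H4 change in group by time, with and without these two terms. Adjustment for severity in H1 and H2, and for caregiving hours anywhere, can be left optional.

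The cost is SAP wording, a few degrees of freedom and a stated rule for missing enrolment scores. No new data are needed and the sample size does not change. Settling this before the data are seen also avoids a post hoc choice of adjustment for the mechanism claim.

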Assessments	Pre-Intervention Assessment	1 week prior to STELLA-FTD start
STELLA-FTD Intervention	Meet with Faculty and Guest Speakers for 8 weekly, 1-hour, sessions	1 week after pre-intervention assessment
Assessment	Mid-intervention Assessment	4 weeks after start of STELLA-FTD sessions
Assessment	Post Assessment 1	Within one week of completion of STELLA-FTD
Assessment	Post-Assessment 2	2 months after end of STELLA-FTD
Assessment	Post-Assessment 3	6 months after end of STELLA-FTD
Weekly Orbit Surveys: Distributed weekly		
Orbit surveys start after enrollment and continue until all surveys are completed		

Measures (Table 3). The primary outcome variable, burden, will be assessed with the 24-item RMBPC (2), which measures the frequency of care recipient behavioral symptoms and care partner reactions to these behaviors. The RMBPC was chosen because it aligns with our theoretical foundation that assumes burden is a result of care partner reactions to behavioral symptoms. The RMBPC has been used in Teri's work (30) and our telehealth

studies, (29, 31, 33, 34) including the STELLA-FTD pilot, allowing for comparison across studies.

Self-efficacy, the mediating variable, will be assessed using Fortinsky's measurement of family care partner self-efficacy for managing dementia (3). We considered the other measures, but Fortinsky's assesses the targets in STELLA-FTD: behavior symptom management and service use.

We will measure care partner preparedness for current and future challenges (63) and personality type to test the effect of a group-based intervention (64).

For care partners in STELLA-FTD+ABC, we will assess the results of the care partners' personalized ABC plans prior to and after the 8-week intervention by collecting data on the frequency of their identified behaviors, and their reactions to them, on their Personalized Target Behavior Survey (29, 30). We will collect data on number of ABC plans each care partner writes on the Orbit weekly survey, weeks 4-36.

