STELLA-FTD contact ⁽²⁹⁾	STELLA-FTD Care Partner contact post intervention
Orbit Survey: Distributed weekly starting Week 5 ⁽²⁹⁾: # of ABC plans (ABC group), service use, burden	

We will implement the above measures using Qualtrics or REDCap Survey Platforms. The surveys will be sent to the Care Partners using these platforms. Auto-reminders will be sent to the Care Partners until they complete the surveys. If they do not complete the surveys within 5 working days, the STELLA-FTD coordinator may call them to identify barriers to completing the surveys. The electronic functionality allows Care Partners to complete surveys in the privacy of their homes, at a time that works for them. The Qualtrics and REDCap platforms are HIPAA compliant and secure. We will assess completion rates and internal consistency of the online platform surveys. Focus group participants will be queried about their experience with the platform.

7) Data and Specimens

a) Handling of Data and Specimens

No biological or genetic specimens will be collected in this study. Data from the measures described above will be collected via the secure Qualtrics or REDCap systems and then downloaded to a secure OHSU file for analyses. Video-recordings of focus groups and intervention sessions to be used for quality assurance and fidelity assessment. Videos not used for these tasks may be deleted. De-identified transcripts of qualitative data will also be downloaded to a secure OHSU file for analysis.

No biological or genetic specimens will be collected in this study. Data from the measures described above will be collected via the secure Qualtrics or REDCap systems and then downloaded to a secure OHSU file for analyses. Video-recordings of focus groups and intervention sessions to be used for quality assurance and fidelity assessment. Videos not used for these tasks may be deleted. De-identified transcripts of qualitative data will also be downloaded to a secure OHSU file for analysis.

b) Sharing of Results with Subjects

If the burden or depression scores indicate severe depression or burden, the Care Partner may be informed, at the discretion of the PI. The Care Partner may be referred to appropriate services if deemed necessary (e.g., social worker or other counseling services). The other results may be provided, if asked, after all data is collected, analyzed and published.

c) Data and Specimen Banking

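### H4 reads a smaller group x time coefficient as mediation, but states no time order and has no self-efficacy score between the start of sessions and the post-intervention burden score

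*Combined protocol and SAP*

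**What the plan says.** **Schedule (section 6, Tables 2 and 3).** Table 3 lists the RMBPC alone under "Mid-Intervention Assessment (Week 8"; Table 2 places that visit "4 weeks after start of STELLA-FTD sessions", halfway through the eight-week programme. The mediator, "Self-efficacy for symptom management and support service use", is listed at weeks 1 and 4. It returns through "Post Assessment 1: Same as Pre-Intervention Assessment Plus" and "Post Assessments 2 & 3: Same as Pre-Intervention Assessment Plus", that is, at about weeks 12, 20 and 36. The weekly Orbit survey does not supply it: its Table 3 entry covers the number "of ABC plans (ABC group), service use, burden".

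**Analysis (section 8).** H1 is a random-intercept model with continuous time. It asks whether the change in reactivity "differs across groups (test vs. control) over the intervention period", with similar analyses at weeks 20 and 36. The visits that make up that period are not listed. For H4, "We will extend the established model in H1 to include total self-efficacy score as a continuous covariate", together with its interaction with time. If the group x time coefficient is smaller than in H1, the plan takes this to indicate a mediated effect. It states no lag, no threshold for the shrinkage, no interval for an indirect effect, no rule for week 8 rows without self-efficacy, and no refit of H1 on the rows used by H4.

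**The concern.** Aim 2 is a directional claim: ABC training raises self-efficacy, and higher self-efficacy lowers burden. The protocol gives the study of mechanism as a reason for the dose-matched control. Within the intervention period, however, no self-efficacy score falls after sessions begin and before the post-intervention burden score. H4 therefore relates change in one to change in the other over the same interval. If training lowered burden directly, and care partners then felt more capable because burden had eased, the group x time coefficient would also shrink once self-efficacy was added. A positive H4 could carry the wrong mechanism into the Stage 2 study that Aim 3 prepares.

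A second, smaller issue is that the H1 coefficient may use week 8 and the H4 coefficient may not. Part of any difference between them could then come from the rows and not from the mediator.

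**Working it through.** **Inputs from the plan (section 4, sample size).** Effect 0.3, three measurements, ICC 0.5 to 0.6, 80% power, alpha 0.05 (taken as two-sided, as in section 8). The stated size reproduces:

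n per arm = 2(1.960 + 0.842)² / 0.3² x (1 + 2 x ICC)/3 = 174.4 x (1 + 2 x ICC)/3

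- ICC 0.5: 116.3, so 117.
- ICC 0.6: 127.9, so 128.

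Both match the plan. The checks below use 128 per arm and ICC 0.6.

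**Step 1. Does attenuation separate the two directions?** Assume no mediation: change in burden = δ x group + error, and change in self-efficacy = -k x (change in burden) + independent error. Let r be the within-arm correlation of the two changes. Regress burden change on group and self-efficacy change:

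- slope on self-efficacy change = -k x Var(burden change)/Var(self-efficacy change)
- group effect on self-efficacy change = -kδ
- adjusted group effect = δ - k²δ x Var(burden change)/Var(self-efficacy change) = δ(1 - r²)

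Expected attenuation is therefore r², with no mediation present: 0.3² = 9% and 0.6² = 36%. Simulation of this change-score analogue of H4 gave median attenuation of about 9% to 37%. The range for r is an assumption, since the documents give none. Another simulation under the same nominal settings gave 3% to 18%, which by the formula corresponds to change correlations of about -0.17 to -0.42 (√0.03 and √0.18). The size depends on r; the direction does not.

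**Step 2. Would week 8 self-efficacy alone help?** A random-intercept model in the form of H4 was simulated with burden driving self-efficacy (weeks 4, 8, 12; 300 care partners; 60 replicates). Mean attenuation was 38% without week 8 self-efficacy and 39% with it. The missing scale is not the main cause; the absence of time order in H4 is.

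**Step 3. Rows.** Suppose self-efficacy enters visit by visit and rows without it are dropped. This is the usual software default, but the plan does not state it. With 300 care partners and complete data:

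| Visits in the model | H1 rows | H4 rows |
|---|---|---|
| 4, 8, 12 | 900 | 600 |
| 1, 4, 8, 12 | 1200 | 900 |
| all six | 1800 | 1500 |

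With balanced data the group x time estimate is Σ(t - t̄)d / Σ(t - t̄)², where d is the group difference at each visit.

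- *Weeks 4, 8, 12.* The weights are -4/32, 0 and 4/32. Week 8 carries no weight, so the change is 0%.
- *Weeks 1, 4, 8, 12.* With week 8, t̄ = 6.25 and Σ(t - t̄)² = 68.75. Without it, t̄ = 5.667 and Σ(t - t̄)² = 64.67. Set the full effect to -1:
  - effect complete by week 8: -(1.75 + 5.75)/68.75 = -0.1091 against -6.333/64.67 = -0.0979, a change of -10.2%
  - effect only from week 12: -5.75/68.75 = -0.0836 against -0.0979, a change of +17.1%
  - linear from week 4 to 12: -(0.5 x 1.75 + 5.75)/68.75 = -0.0964 against -0.0979, a change of +1.6%

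The early-response case yields about 10% apparent attenuation with no mediation; the late-response case would hide some. Using all six visits gives +2.3% (linear), +15.0% (early) and -8.0% (late). With weeks 4, 8, 12 and 15% loss after week 8, simulated eight-week effects were -0.308 against -0.300 (early) and -0.292 against -0.302 (late), about 3% either way.

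**The case against.** **The later visits do provide order.** A reader might infer that the trial can never place self-efficacy before burden. The documents do not support that: Post Assessment 1 self-efficacy precedes reactivity at weeks 20 and 36, and similar analyses are planned there. This stands, and it confines the point to the intervention period. But no lagged model is specified, and one using these visits would address later burden, not change during training.

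**H2 gives some protection.** A reader might also infer that a reverse-causation trial would look the same as mediation throughout. It usually would not. With δ = 0.3 and SD of change √(2 x 0.4) = 0.894, the standardised burden effect is 0.335, so the group effect on self-efficacy change is 0.335r, or 0.10 to 0.20 SD. With 128 per arm, H2 would then be significant in only about 12% to 36% of trials. This also stands, although the plan lists H2 as step one without making the reading of H4 conditional on it.

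**A lagged model through week 8 is not a clean answer.** One could regress week 12 reactivity on week 8 self-efficacy, adjusting for earlier self-efficacy and for week 4 and week 8 reactivity. Week 8 reactivity lies on the pathway and can absorb mediation already achieved. With full mediation acting at the same visit (assumed self-efficacy effects of 0.25 SD at week 8 and 0.5 SD at week 12), the lagged term was significant in about 5% of simulated trials, no better than chance. It would do better if mediation took weeks to act, but no document supports a particular lag. This stands and shapes the fix.

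**The row mismatch is minor and conditional.** True for complete data at weeks 4, 8 and 12. It cannot be dismissed altogether, because the visits in the H1 model are not listed.

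**Conclusion.** The point holds in a limited form. Within the intervention period, H4 has no mediator score after sessions start and before the post-intervention outcome, states no lag, and treats any shrinkage of group x time as mediation. With burden driving self-efficacy and no mediation, expected attenuation equals the squared correlation of changes: about 9% to 37% in simulation for assumed r of -0.3 to -0.6, and less if the correlation is weaker. Attenuation alone therefore does not show mechanism.

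It would be too strong to blame the missing week 8 scale by itself, since attenuation is nearly the same with it (39% against 38%). The row mismatch is nil for complete weeks 4, 8 and 12, and about -10% to +17% only if week 1 is included, rows are dropped, and the response is non-linear. Nothing here touches the H1 test or Aim 1. The weakness lies in the causal reading of Aim 2, and it should be corrected before the analysis is fixed.

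**What to change.** 1. **Common rows.** List the visits in each model, and refit H1 on exactly the rows used for H4 before comparing coefficients. Cost: analysis wording.
2. **Replace the attenuation or loss-of-significance rule** with an estimated indirect effect and a bootstrap confidence interval, resampling care partners. This puts uncertainty on the result; it does not by itself settle direction. Cost: analysis wording and programming.
3. **Prespecify a time-ordered analysis from data already planned**, for example Post Assessment 1 self-efficacy against reactivity at weeks 20 and 36. Describe the concurrent H4 result as an association consistent with mediation. No new data are needed. Unmeasured confounding of mediator and outcome remains and should be acknowledged.
4. **Add the 10-item self-efficacy scale to the week 8 electronic survey**, so that order can also be examined during training. Cost: ten items at an existing contact and a small respondent burden, with no extra visit. Scores not collected at week 8 cannot be recovered later; if that collection has closed for some cohorts, items 1 to 3 still apply.

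Do not make the lagged model that adjusts for week 8 reactivity the sole test of H4. Use it at most as a sensitivity analysis, with the caution that it can miss mediation already achieved by week 8.
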